10.2 Statistical Hypotheses

Primary Endpoints

Efficacy: 6 minute walk distance (6MWD)

Hypothesis: Degree of improvement in 6MWD will be greater in participants assigned to mHealth-CR than in those assigned to usual care.

Engagement: Mobile health (mHealth) use

CONFIDENTIAL

This material is the property of the NYU School of Medicine and Langone Medical Center. Do not disclose or use except as authorized in writing by the study sponsor

Hypotheses: (1) Among participants offered mHealth-CR, there will be distinct trajectories of engagement (e.g., sustained engagement, disengagement, reengagement, deteriorating engagement); and (2) there will be significant differences in participant characteristics among these groups.

Secondary Endpoints

1. Goal attainment (measured by Goal Attainment Scaling)
2. Health status (measured by SF-12 and SAQ)
3. Activities of daily living (ADLs)
4. Hospital readmission
5. Death

Hypotheses: Goal attainment scaling, health status, and ADLs will improve in participants who are offered mHealth-CR compared with usual care. Hospital readmission and death will be lower in participants who are offered mHealth-CR compared with usual care.

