10.4 Description of Statistical Methods

10.4.1 General Approach

Statistical comparisons will be performed using two-sided significance tests and two-sided confidence intervals. We will begin all analyses with descriptive summary statistics and graphical displays of all variables, with attention to assessing balance in these characteristics by intervention group, and with assessment of the distribution of variables, relevant to the choice of statistical tests.

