10.4.2 Analysis of the Primary Efficacy Endpoint(s)

6MWD

We will assess the difference in 6MWD by calculating difference scores for each participant and comparing the intervention and usual care groups with an independent group t-tests allowing for unequal variances. We will also regress 3-month 6MWD on a binary indicator of treatment group, with adjustment for baseline 6MWD and the stratification factor (enrollment site). While randomization should obviate the need for additional adjustment, we will explore whether adjustment for participant-level characteristics (e.g., demographic factors or referral to ambulatory CR) is necessary, using the change-in-estimate criterion. We realize that engagement with the mHealth-CR program may also affect attendance and engagement with structured ambulatory CR programs. We intend to explore this as a mediator of the effect of assignment to the intervention arm. We will use structural equation models to estimate the direct and indirect effects of mHealth, where the direct effect is that of mHealth-CR on the 6MWD, and the indirect effect is mediated through attendance at structured ambulatory CR.

Engagement

We hypothesize that (1) among participants offered mHealth-CR, there will be distinct trajectories of engagement (e.g., sustained engagement, disengagement, reengagement, deteriorating engagement); and (2) there will be significant differences in participant characteristics among these groups. While our aim is largely exploratory (given the paucity of data on mHealth-CR engagement), we will test whether the following characteristics are significant: age (≥ 80 years), sex, race/ethnicity, comorbidity burden (≥ 2 chronic medical conditions), frailty, social support (based on living alone), cognitive impairment (based on Mini-Cog), and depressive symptoms (based on PHQ-8). We selected these factors based on literature related to engagement in other technologies. We will conduct latent class analysis to identify profiles of engagement and explore whether these factors indicate membership in a class; these models use maximum likelihood estimation,

CONFIDENTIAL

This material is the property of the NYU School of Medicine and Langone Medical Center. Do not disclose or use except as authorized in writing by the study sponsor

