10.4.5 Adherence and Retention Analyses

Adherence (termed engagement in our study, which is more reflective of patients' use of mHealth interventions) is a prespecified endpoint in our trial. To measure engagement with the assigned treatment strategy we will perform the following analyses:

- (1) Engagement with mHealth-CR: The mHealth-CR intervention includes a number of activities expected of participants randomized to this arm. The primary engagement endpoint is an 11-point score, tabulated weekly, indicating completion of each component of the mHealth-CR intervention: (1–7) daily entry of exercise data and rated perceived exertion (1 point for each day with total possible 7 points per week); (8) completed phone call with exercise therapist; (9) at least one electronic communication with exercise therapist; (10) watching educational video (which will vary by week); and (11) at least one home BP measurement. Engagement will be assessed as a pseudo-continuous outcome, as the score can range from 0% (0 activities completed) to 100% (all 11 activities completed).

Participant engagement is a primary endpoint of the study. We will conduct latent class analysis to identify profiles of engagement and explore whether these factors indicate membership in a class; these models use maximum likelihood estimation, implemented with the iterative EM algorithm, to identify a latent class solution for the set of indicators. We will evaluate model fit using the G2 statistic and compare models with the likelihood-difference test for nested models and the Akaike and Bayesian information criteria (AIC, BIC) for non-nested models. While we have identified four potential classes a priori, we will use the parametric bootstrap likelihood ratio test to select the optimal number of classes supported by the data in conjunction with the AIC and BIC. The output of the model will be a set of "item-response" probabilities giving the likelihood of a particular characteristic within each latent class, and a set of posterior predicted probabilities of latent class membership; uncertainty in predicting class membership will be summarized using the odds of correct classification (OCC) diagnostic tool.

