10.4.9 Multiple Comparison/Multiplicity

Not applicable as there is one primary efficacy endpoint.

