10.5 Sample Size

We will randomize 400 participants using a 3:1 allocation, resulting in 300 participants in the intervention group and 100 participants in the usual care group. While we will aim to minimize participant dropout, we include adjustment for up to 20% dropout in each arm, resulting in about 320 participants with evaluable endpoints (240 intervention, 80 usual care). We wish to be able to detect a clinically meaningful difference between groups in our primary efficacy endpoint, change in 6MWD from baseline to 3 months. A recent meta-analysis⁵⁷ found an average difference in 6MWD of about 60 meters before and after traditional CR. Perera et al. determined this degree of change in 6MWD to be clinically meaningful based on its relationship to other health status measures.⁹⁸ Minneboo et al., however, also estimated an improvement in 6MWD in a control group of approximately 35 meters.⁵⁹ We therefore require adequate power to detect a difference between groups of less than 25 meters in change in 6MWD (i.e., the difference between a 60-meter improvement in the intervention group and a 35-meter improvement in the usual care group); this is the same amount estimated by Gremeaux et al. as a minimal clinically important difference in patients with IHD.⁹⁹ Assuming a conservative standard deviation estimate of 60 meters,⁵⁷ 320 participants provide approximately 90% power to detect a difference between groups of 25 meters, using a two-sided, 0.05-level test; there is 80% power to detect a difference

CONFIDENTIAL

This material is the property of the NYU School of Medicine and Langone Medical Center. Do not disclose or use except as authorized in writing by the study sponsor

between groups as small as 22 meters. This sample size also provides at least 80% power to detect reasonable effect sizes in secondary endpoints.

While the sample size was determined to provide sufficient power to detect a clinically meaningful difference in the primary outcome of 6MWD, it enables comparisons of secondary efficacy endpoints as well. The table below shows clinically meaningful effect sizes for these outcomes, and gives the power to detect these effect sizes

CONFIDENTIAL

This material is the property of the NYU School of Medicine and Langone Medical Center. Do not disclose or use except as authorized in writing by the study sponsor

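### Age and comorbidity enter the engagement analysis as unexplained yes/no cuts, which discards information the trial already collects; the eight factors are better reported as estimates than as significance claims

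*Combined protocol and SAP*

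**What the plan says.** All references are to the combined protocol and SAP.

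- Section 10.2 states, as the second engagement hypothesis, that "there will be significant differences in participant characteristics among these groups". The groups are the engagement trajectories.
- Section 10.4.2 (Engagement) opens the relevant sentence with "While our aim is largely exploratory (given the paucity of data on mHealth-CR engagement" and continues "we will test whether the following characteristics are significant: age (≥ 80 years), sex, race/ethnicity, comorbidity burden (≥ 2 chronic medical conditions". The list ends with "frailty, social support (based on living alone), cognitive impairment (based on Mini-Cog), and depressive symptoms (based on PHQ-8". Counting race/ethnicity as one, that makes eight characteristics.
- The same section cites literature for the choice of these factors. It gives no reason for the cut-points at 80 years and at two conditions, and it does not say which conditions count.
- Section 10.4.5 says: "Participant engagement is a primary endpoint of the study".
- Section 10.4.9, on multiplicity, reads in full: "Not applicable as there is one primary efficacy endpoint".
- Section 10.4.1 fixes sidedness only: "Statistical comparisons will be performed using two-sided significance tests and two-sided confidence intervals". No significance level is written for the eight characteristics. The 0.05 level is written for the 6MWD comparison and the secondary outcomes in section 10.5.
- Age and date of birth are in the screening extract (section 5.4.1), and a 16-item history of conditions and habits is abstracted at baseline (section 7.1.1).

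**The concern.** A yes/no split treats a 66-year-old and a 79-year-old as the same, and a patient with two conditions like one with seven. If engagement changes gradually with age or disease burden, the analysis then has less chance of seeing it, and the estimate is harder to use. Section 2.2 says the trial should help identify who is suited to future mHealth programmes, so weak or missed predictors have a practical cost. The data needed to avoid this are already collected. For systolic blood pressure, section 10.4.11 itself prefers comparing means to choosing a threshold.

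A second, smaller matter is how the results will be worded. The plan describes the aim as mainly exploratory, yet frames the hypothesis in terms of significance under an endpoint it calls primary, and gives neither a level nor a rule for the set of eight. A reader of the results would not know how to weigh one factor with a small p-value.

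**Working it through.** **1. The plan's own design figure.** The documents give no power or error rate for the engagement predictors. The nearest figure is for the primary efficacy endpoint: "320 participants provide approximately 90% power to detect a difference between groups of 25 meters, using a two-sided, 0.05-level test". With 240 and 80 evaluable and SD 60 m, the standard error is 60 × √(1/240 + 1/80) = 7.746 m. Power at 25 m is Φ(25/7.746 − 1.960) = Φ(1.268) = 89.8%. At 22 m it is Φ(22/7.746 − 1.960) = 81.1%. Both agree with the stated 90% and 80%. Nothing below alters them.

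**2. Information kept by the age cut.** For a linear effect, the information kept is the squared correlation between the indicator and the uncut variable. Let p be the share aged 80 or over. The documents do not give p, so 10% to 30% is assumed. Two shapes for age are shown, because entry at 65 truncates the distribution.

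- Normal shape: φ(c)² / [p(1 − p)], with c the normal quantile that leaves p above it. At p = 0.20, c = 0.842 and φ(c) = 0.280, so 0.0784 / 0.16 = 0.490.
- Exponential decline from 65: p·c² / (1 − p), with c = −ln p. At p = 0.20, c = 1.609, so 0.20 × 2.590 / 0.80 = 0.648.

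| Assumed share aged ≥ 80 | Kept, normal | Equivalent of 300 | Kept, exponential | Equivalent of 300 |
|---|---|---|---|---|
| 10% | 0.342 | 103 | 0.589 | 177 |
| 20% | 0.490 | 147 | 0.648 | 194 |
| 30% | 0.576 | 173 | 0.621 | 186 |

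The 300 is the planned number randomized to mHealth-CR (section 10.5). For comparison, a median split of a normal variable keeps 0.637.

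**3. What that means for power.** Take an age effect that would have 80% power uncut in a single two-sided 5% test, so its standardized size is 1.960 + 0.842 = 2.802. After a cut that keeps 0.490, power is Φ(2.802 × √0.490 − 1.960) = 50%. After a cut that keeps 0.648, it is Φ(2.802 × √0.648 − 1.960) = 62%. These are one-parameter approximations. The class model has several classes and uncertain membership, so they show the order of the loss and do not forecast the trial's power.

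**4. Comorbidity.** The same loss arises in principle, but no figure is given. The documents state neither the share with two or more conditions nor which of the 16 items count, and the normal formula suits a small count poorly.

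**5. The set of eight.** Assume one test per factor at 5%.

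- All eight null and independent: 1 − 0.95⁸ = 33.7%, with 8 × 0.05 = 0.4 false positives expected.
- All eight null, equally correlated test statistics (simulated): 31.9% at correlation 0.2, 30.0% at 0.3, 25.0% at 0.5, 15.7% at 0.8.
- Four of the eight null, independent: 1 − 0.95⁴ = 18.5%.

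**The case against.** The best defence is that this is a within-arm analysis, declared mainly exploratory in the very sentence that lists the factors, and that strict error control is not usual there. That stands. It argues against demanding a correction such as Holm, and it is a reason to report estimates. It does not explain the cuts, because an exploratory analysis also gains from using the full variable.

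A second defence is that the loss depends on shape. If engagement truly steps at age 80, the cut loses nothing, and a right-skewed age distribution makes the loss smaller than the normal formula suggests. Both remarks are fair, and the range in the working reflects the second. The documents offer no evidence for a step.

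Several stronger readings are tempting, and the documents do not support them:

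- A reader might infer that each factor is tested at 5%. No level and no per-factor test is written for these characteristics.
- A reader might infer that a false predictor is likely. About one in three is the figure when all eight are null and independent, and it falls with positive correlation or real effects.
- A reader might infer that the comorbidity indicator barely varies in this population. Its prevalence is not in the documents.
- A reader might infer that the cuts waste the 3:1 allocation. Section 10.6.1 justifies that allocation by estimation of the trajectories, which come from weekly engagement scores and are not affected by how two covariates are coded.
- A reader might infer that all the graded factors are dichotomized. No cut-point is given for PHQ-8 in section 10.4.2.
- A reader might infer that section 10.4.9 is wrong. It speaks only of efficacy, and for efficacy its count of one primary endpoint is correct. It is simply silent on engagement.

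**Conclusion.** The point holds as an inexpensive improvement to the engagement analysis. Two of the eight predictors are cut without a stated reason. For age, the cut keeps roughly 34% to 58% of the information under a normal shape and 59% to 65% under an exponential one. This rests on an approximately linear relation and an assumed 10% to 30% of participants aged 80 or over. The loss for comorbidity cannot be sized from the documents.

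On multiplicity, the documents support a narrower conclusion: the exploratory description and the significance wording under a primary label do not fit together, and the reporting should follow the former. The 34% figure is conditional on an assumed 5% level, one test per factor, and all eight factors null and independent. It does not show that a spurious finding is to be expected. The randomized 6MWD comparison is not touched.

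**What to change.** - In section 10.4.2, enter age in years and the number of chronic conditions as continuous covariates of class membership. Define in advance which items of the abstracted history count as conditions. Add a simple linearity check for both terms, and keep the cuts at 80 years and two conditions for display tables only. If the cuts are to stay in the model, give the reason for each.
- In sections 10.2 and 10.4.2, say that the eight characteristics are reported as estimates with confidence intervals and without a claim of significance. Add one sentence to section 10.4.9 saying the same, so that its silence on engagement is not left to interpretation.

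The cost is wording in the SAP and no new data. The downsides are the linearity check and a slightly less simple presentation than a yes/no comparison.

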4.2 Study Endpoints

4.2.1 Primary Study Endpoints

Primary Efficacy Endpoint. The primary endpoint of this study is the change in the 6MWD between the baseline visit and 3-month follow-up visit. Change in 6MWD, reflective of functional capacity, is measured by the 6-minute walk test (6MWT). The 6MWT will be performed during baseline hospitalization and at the 3-month follow-up visit by a blinded research nurse or exercise therapist.

Primary Engagement Endpoint. Our main measure of engagement is weekly percent completion of the mHealth-CR program. Completion of mHealth-CR analyzed at weekly intervals will allow us to determine distinct engagement trajectories over the 3-month study period. Weekly engagement will be measured as the fraction of the following 11 elements completed each week: (1–7) daily entry of exercise data and RPE; (8) completed weekly phone call with exercise therapist; (9) at least one electronic communication with exercise therapist; (10) watching educational video (which will vary by week); and (11) at least one home BP measurement. Engagement will be assessed as a pseudo-continuous outcome, as the score can range from 0% (0 activities

CONFIDENTIAL

This material is the property of the NYU School of Medicine and Langone Medical Center. Do not disclose or use except as authorized in writing by the study sponsor

completed) to 100% (all 11 activities completed). We will also explore determination of a threshold for minimally sufficient engagement that is associated with improved outcomes.

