6.1.3 Assessment of Subject Compliance with Study Intervention

Assessments of compliance to assigned treatment strategies will be conducted through the following:

- (1) *Receipt of traditional CR:* Participants in both arms will receive standard referral to traditional (ambulatory) CR. We will summarize the uptake of this referral using attendance at initial and

CONFIDENTIAL

subsequent CR program visits.

(2) *Engagement with mHealth-CR*: The mHealth-CR intervention includes a number of activities expected of participants randomized to this arm. The primary engagement endpoint is an 11-point score, tabulated weekly, indicating completion of each component of the mHealth-CR intervention: (1–7) daily entry of exercise data and rated perceived exertion (1 point for each day with total possible 7 points per week); (8) completed phone call with exercise therapist; (9) at least one electronic communication with exercise therapist; (10) watching educational video (which will vary by week); and (11) at least one home BP measurement. Engagement will be assessed as a pseudo-continuous outcome, as the score can range from 0% (0 activities completed) to 100% (all 11 activities completed).

(3) *Use of Fitbit*: Participants in the intervention arm will receive a Fitbit monitor, and data will be evaluated on a weekly basis to evaluate whether they are consistently using the device.

7 Study Procedures and Schedule

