7.1 Study Procedures/Evaluations

7.1.1 Study Specific Procedures

Study procedures can be seen in Table 1.

Table 1. Schedule of Study Activities

	Baseline	Weekly	Ambulatory follow-up
Study Week (approximate)	0	1-12	12
Informed Consent	X		
Demographics	X		
Height	X		
Weight and Blood Pressure	X		X
6 Minute Walk Test	X		X
Short Form 12 (SF-12)	X		X
Seattle Angina Questionnaire 7 (SAQ-7)	X		X
Activities of Daily Living (ADLs)	X		X
Mini-Cog	X		
Goal Attainment Scaling (GAS)	X		X
Depression (PHQ-8)	X		X
Frailty Elements	X		X
Chart abstraction (comorbidities, medications, laboratory/cardiac test results)	X		
Randomization	X		
Education on cardiac risk factor management	◊		
Ascertainment of home environment and barriers to mobility	◊		
Introduction to mHealth-CR software	◊		
Personalized exercise plan	◊		
Daily passive activity monitoring (Fitbit)		◊	
Daily therapist-directed activity (walking, upper extremity resistance training)		◊	
Daily mHealth data entry		◊	
Weekly exercise therapist phone call		◊	

CONFIDENTIAL

This material is the property of the NYU School of Medicine and Langone Medical Center. Do not disclose or use except as authorized in writing by the study sponsor

Weekly blood pressure measurement		◊	
Weekly video education		◊	
Hospital readmissions (questionnaire)			X
Chart abstraction (hospital readmission verification, attendance at traditional CR)		Week 8	X
		Biweekly/ Monthly	
Phone assessment of ADLs		X	

X = All participants ◊ = Intervention participants only

CONFIDENTIAL

This material is the property of the NYU School of Medicine and Langone Medical Center. Do not disclose or use except as authorized in writing by the study sponsor

- *Chart Abstraction* will be performed by the research coordinator. Elements will be entered into a secure Research Electronic Data Capture (REDCap) database created by NYU DataCore.
 - Medical history/comorbidities: hypertension, diabetes, heart failure, peripheral artery disease, atrial fibrillation, cancer, chronic lung disease, obesity, chronic kidney disease, chronic liver disease, gastrointestinal bleeding, cerebrovascular disease, dementia, osteoarthritis, tobacco use, alcohol use.
 - Outpatient medications.
 - Laboratory data: hemoglobin, platelet count, white blood cell count, sodium, potassium, BUN, creatinine, glucose, troponin (all based on admission blood draw). Peak troponin value will also be abstracted.

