implemented with the iterative EM algorithm, to identify a latent class solution for the set of indicators. We will evaluate model fit using the G^2 statistic and compare models with the likelihood-difference test for nested models and the Akaike and Bayesian information criteria (AIC, BIC) for non-nested models. While we have identified four potential classes a priori, we will use the parametric bootstrap likelihood ratio test to select the optimal number of classes supported by the data in conjunction with the AIC and BIC. The output of the model will be a set of “item-response” probabilities giving the likelihood of a particular characteristic within each latent class, and a set of posterior predicted probabilities of latent class membership; uncertainty in predicting class membership will be summarized using the odds of correct classification (OCC) diagnostic tool.

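### G-squared, the only absolute-fit measure named for the engagement latent class model, has essentially no power under its usual chi-square reference, and the class-enumeration tools do not fill that gap

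*Combined protocol and SAP*

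**What the plan says.** Section 4.2.1 makes weekly completion of the mHealth-CR programme the primary engagement endpoint: "Weekly engagement will be measured as the fraction of the following 11 elements completed each week". It adds: "Engagement will be assessed as a pseudo-continuous outcome". Table 1 in Section 7.1.1 shows weekly activities over study weeks 1 to 12.

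Section 10.4.2 (Engagement) plans a latent class analysis. On fit it says: "We will evaluate model fit using the G^2 statistic and compare models with the likelihood-difference test for nested models", with AIC and BIC for non-nested models. Four classes are proposed in advance, but their number is to be settled empirically: "we will use the parametric bootstrap likelihood ratio test to select the optimal number of classes supported by the data in conjunction with the AIC". The other information criterion, BIC, is used too. Posterior class probabilities and the odds of correct classification then summarise membership. Section 10.4.5 repeats the fit sentence: "We will evaluate model fit using the G2 statistic and compare models with the likelihood-difference test for nested models".

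Three things are not stated: which variables are the indicators, how the weekly score is coded for the model, and what distribution G-squared is referred to. The bootstrap is named only for choosing the number of classes.

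**The concern.** G-squared compares observed counts with model-expected counts over the full cross-table of the indicators. Its usual reference is chi-square with (cells − 1 − parameters) degrees of freedom, and this needs reasonable expected counts per cell. Twelve weekly indicators spread a few hundred people over thousands to trillions of cells. The statistic then falls far below its nominal degrees of freedom whether or not the model is right.

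The other planned tools rank class models against each other. All of those models assume that weeks are independent within a class. If engagement carries over from one week to the next, extra classes can be used to absorb that dependence. No stated check would show that the selected solution is an artefact.

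At stake are the first engagement hypothesis (that distinct trajectories exist), the tests of participant characteristics by class, and the interpretation of the engagement categories that also guide focus-group sampling in Section 10.4.11.

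**Working it through.** **Inputs.** 400 randomised 3:1 with 20% dropout per arm (Section 10.5); 11 weekly elements, hence 12 possible scores (Section 4.2.1); 12 weeks (Table 1). The plan gives no figure for the fit test. Its arm sizes reproduce: 400 × 3/4 = 300, and 300 × 0.8 = 240.

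**Cells and degrees of freedom.** For L levels per week and C classes, cells = L^12 and df = L^12 − 1 − [(C − 1) + 12C(L − 1)].

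- Yes/no weeks: 2^12 = 4,096 cells; 300/4,096 = 0.073 people per cell. df = 4,096 − 1 − 12 = 4,083 for one class, and 4,096 − 1 − 51 = 4,044 for four.
- Three levels: 3^12 = 531,441 cells; one-class df = 531,416.
- Full 12-level score: 12^12 ≈ 8.9 × 10^12 cells.

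**Largest possible G-squared for a one-class model.** It cannot exceed 2N × 11 × ln L. With N = 300:

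- L = 3: 600 × 11 × 1.0986 = 7,251, against a 5% critical value of about 533,113. No data set can fail.
- L = 12: 600 × 11 × 2.4849 = 16,400, on about 9 trillion df. No data set can fail.
- L = 2: 600 × 11 × 0.6931 = 4,575, against 4,233. Failure is possible only near the extreme where half the participants engage every week and half never do. With N = 240 the bound is 3,660, and failure is impossible.

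**Yes/no weeks, simulated.** Data came from four assumed trajectory classes. Chi-square G-squared rejected none of the models fitted with too few classes:

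| Model fitted | df | Mean G-squared, N = 300 | Mean G-squared, N = 240 | Rejected |
|---|---|---|---|---|
| One class | 4,083 | 1,828 | 1,464 | 0% |
| Two classes | 4,070 | 771 | 639 | 0% |

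In one such data set (N = 300) the one-class G-squared was 1,894. Its parametric-bootstrap distribution under a true one-class model had mean 718 and range 600 to 805. So a correct model also sits far below 4,083, and the bootstrap reference rejects the wrong one (p = 0.01, the minimum with 99 samples).

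**Do the enumeration tools cover this?** For too few classes, yes. In the same data set the bootstrap likelihood ratio statistic for one against two classes was 1,122.9, against a bootstrap maximum of 41.0. In 20 further four-class data sets it rejected one against two and two against three classes 20 times out of 20, and BIC chose three or four classes.

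For a selected model that misfits, no. Data were simulated from one homogeneous population with no classes. Each week a person repeats last week's status with probability s, otherwise redraws it with 60% engaged (N = 300, 20 data sets per row, up to six classes, 19 bootstrap samples):

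| s | Classes chosen by BIC | Chi-square G-squared rejects | Bootstrapped G-squared rejects | Adjacent-week residuals reject |
|---|---|---|---|---|
| 0.3 | 2–3 | 0% | 45% | 100% |
| 0.5 | 4–6 | 0% | 90% | 100% |
| 0.7 | 5–6 | 0% | 100% | 100% |

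A separate run on data of this kind gave 2 to 5 classes by BIC, no chi-square rejections, and 50% to 90% rejection by bootstrapped G-squared. The bootstrap likelihood ratio test was not run on these data. It compares K with K + 1 classes under the same independence assumption, so it is not a check of absolute fit.

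**The case against.** A reader might infer that under this plan every model, however wrong, would pass. The documents do not support that. The same paragraph chooses the number of classes by bootstrap likelihood ratio test with AIC and BIC, and those tools caught the too-small models above. No step accepts a model because G-squared is non-significant, and class membership comes from posterior probabilities. Even for G-squared alone the claim is not literally true, as the extreme yes/no case at N = 300 shows.

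A reader might also infer that the plan commits to the chi-square reference and to a 12-way cross-table. It states neither. A bootstrap or purely descriptive use of G-squared is not excluded, and a pseudo-continuous score may be modelled as continuous, in which case the cell counts do not apply.

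Both objections stand as limits on the point, but they do not remove it. Choosing well among class models differs from checking that the chosen one describes the data, and G-squared is the only tool named for the second task. On the continuous reading, that tool is undefined and no absolute-fit check is left. Finally, Section 10.4.2 itself treats the engagement aim as mainly exploratory, and no efficacy conclusion depends on it. That limits the weight of the point.

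**Conclusion.** The point holds in this form. Under the usual chi-square reference, G-squared cannot reject a one-class model at all for weekly scores with three or more levels. It rejected none of the misfitting models simulated with yes/no weeks. The bootstrap likelihood ratio test, AIC and BIC protect against too few classes, but not against a selected model that misfits through dependence between weeks, which can itself produce spurious classes.

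The cell counts, degrees of freedom and upper bounds need only 12 weekly indicators, categorical coding and 240 to 300 participants. The rejection rates also rest on assumed trajectories and carry-over strengths, on yes/no coding, and on 20 data sets per row in the carry-over table, so those percentages are approximate. The strength of carry-over in this trial is unknown.

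This is a modest but worthwhile improvement to the analysis of an endpoint labelled primary. The 6MWD analysis is unaffected.

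**What to change.** In Sections 10.4.2 and 10.4.5:

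- State the indicators of the latent class model and how the weekly score is coded (yes/no, ordered categories or continuous).
- For categorical coding, replace the fit sentence with wording such as: *Absolute fit of the selected model will be judged by a parametric-bootstrap p-value for G-squared and by residual associations between pairs of weeks, especially adjacent weeks. G-squared will not be referred to the chi-square distribution.*
- For continuous modelling, compare observed with model-implied weekly means, variances and covariances instead of using G-squared.
- Keep the bootstrap likelihood ratio test, AIC and BIC for the number of classes.

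The residual check should carry at least equal weight. It detected the carry-over in every simulated data set, while the bootstrapped G-squared was examined only for yes/no weeks. With the 12-level score every simulated participant had a unique pattern, and its performance there was not tested.

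The cost is SAP wording and computing time. The bootstrap machinery is already planned and no new data are needed. The change should be made before the engagement data are analysed.
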